6.11.1.2. Neurocognitive Analyses

Compliance rate will be calculated as the number of completed or prorated questionnaires divided by the number of expected questionnaires given those that are still on study. For Trail Making Tests A and B, patients with completed and prorated tests will be included in analysis. A test score can be prorated if test was discontinued or maximum time was used due to a neurological difficulty.

Each neurocognitive test will be converted to a standardized score (mean = 0, SD = 1) using published healthy control data. To prorate discontinued Trail Making Tests A and B, the raw scores will be divided by the number of circles correctly completed and then multiplying the resulting "time per circle" figure by 25. [Wefel et. al. 2011; Heaton RK et. al. 2004]. For each neurocognitive test, standardized scores will be summarized at each assessment. Repeated measures ANOVA will be performed for each measure to assess the mean differences in change from baseline standardized scores between treatment arms, adjusting for baseline score if needed. The change in standardized score from baseline will be calculated and using the Reliable Change Index (RCI) [Wefel et. al. 2011], the neurocognitive status over time will be categorized into improved, stable or decline. The RCI is a threshold that measures improvement or decline in neurocognitive function and represents a 90% confidence interval for the difference in raw score between baseline and the next assessment assuming no real change occurred. It is derived as follows:

$RCI = 1.64 (SEdiff)$ where $SEdiff = [2(SEM^2)]^{1/2}$ and $SEM = SD_1[(1 - r_{xy})^{1/2}]$

where $SEdiff$ is the standard error of difference in raw score from baseline to the next assessment, SEM is the standard error of measurement, SD is the standard deviation, and r_{xy} is the test-retest reliability statistic. All derived RCI will be rounded to the nearest whole number and compared with changes from baseline assessments to determine the change in neurocognitive status. Those changes that did not meet the RCI threshold will be considered stable performance. Any changes from baseline neurocognitive status showing improvement or decline will need to be confirmed at the next assessment if available. In the absence of a confirmatory assessment, any sign of improvement or decline in neurocognitive status will be deemed as stable.

The proportion of patients with number of tests indicating stable, improved or decline in neurocognitive status will be summarized at each assessment by treatment arm.

The relationship between survival/tumor response and change in cognitive function will also be assessed in subgroups of patients with $PFS > 6$ months, $OS > 12$ months and patients with objective response. Proportion of patients in the above subgroups showing stable or improvement on all neurocognitive tests, or decline on at least one test at the time of PFS (at 6 months), OS (at 12 months) or at time of response will be provided and summarized for each treatment arm. Significant p-values comparing the proportion of patients with stable or improved tests on all tests will be reported.

The proportion of time patients spent in a stable/improved neurocognitive function during 6 months progression-free or 12 months survival will be assessed for each treatment arm. The area under the curve, where x-axis is the progression-free or survival time and y-axis is neurocognitive state will be used to calculate this proportion for individual patient.

Differences in neurocognitive progression (RCI determined) will be assessed between arms using Cox proportional hazards regression and adjusting for covariates such as use of psychostimulants, steroids, anti-epileptic medications, etc). Neurocognitive progression duration is measured from randomization to the time of RCI determined neurocognitive decline or death from any cause.

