10.2. Health Outcome Measures

Patient symptoms will be measured with the self-administered MDASI-BT ([Attachment 8](#)). Neurocognitive function will be measured by the HVLT-R, the Trail Making Test, Parts A and B, and COWA. The details of the neurocognitive test administration and implementation will be provided separately from the protocol during training.

The MDASI-BT and the neurocognitive function assessments will be completed at baseline, at the same time of the disease assessments (ie, MRI) post-baseline, and after discontinuation of study therapy.

The health outcome measures should be completed at the beginning of office visits, before any extensive contact and consultation with the clinician/study investigator in regards to the disease assessments. Consultation with the clinician may bias perceptions about symptoms and thus affect assessments. The MDASI-BT, Trail Making Test Parts A and B, and COWA can be completed during the 20-minute wait before the delayed recall for the HVLT-R; as a result of the

delayed recall, the total time for administration of health outcome measures will be approximately 25 minutes.

The health outcome measures will only be completed by patients for whom there is a valid translation in which the patient is fluent.

The neurocognitive assessments will be completed where training is available and feasible.

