Relative Day Within a Cycle	1±2	6±2	12±2	26±2	
Treatment					
Lomustine					
LY2157299 monohydrate or matched placebo	X	X	X		
Procedures					
Physical examination	X				
Vital signs (heart rate, blood pressure)	X				
CTCAE	X				
Concomitant medications	X				
ECOG performance status	X				
Health outcome measures				X	
Echocardiography with Doppler				X	
ECG				X	
PFT				X	
Troponin I and BNP				X	
Hematology				X	
Fox P3				X	

CCI

Cycle	Cycles 3, 6, 9, 12				Comments
Relative Day Within a Cycle	1±2	6±2	12±2	26±2	
Serum chemistry				X	
ECG chemistry				X	
Serum hs-CRP				X	
Radiological tumor assessment				X	
Chest CT scan or chest MRI				X	
MAP				X	
Affymetrix				X	

CCI

Study Schedule for Protocol H9H-MC-JBAL – Cycles 4, 7, 10, Visit 801, Follow-Up

Cycle	Cycles 4, 7, 10				Visit 801	Follow Up	Comments
Relative Day Within a Cycle	1±2	6±2	12±2	26±2			
Treatment							
Lomustine		X					
LY2157299 monohydrate or matched placebo	X	X	X				
Procedures							
Physical examination	X				X		
Vital signs (heart rate, blood pressure)	X				X		
CTCAE	X				X		
Concomitant medications	X				X		
ECOG performance status	X				X		
Health outcome measures				X	X		
Echocardiography with Doppler				X	X	X	
ECG				X	X	X	
Troponin I and BNP				X	X		

Hematology				X	X	CC1	
Cycle	Cycles 4, 7, 10				Visit 801	Follow Up	Comments
Relative Day Within a Cycle	1±2	6±2	12±2	26±2			
Urinalysis				X	X		
Serum chemistry				X	X		
ECG chemistry				X	X	X	
Fox P3				X			
Serum hs-CRP				X			
Radiological tumor assessment				X			
MAP				X			
Affymetrix				X			

Abbreviations: BNP = brain natriuretic peptide; COWA = Controlled Oral Word Association; CSF = cerebrospinal fluid; CT = computed tomography; CTCAE = Common Terminology Criteria for Adverse Events; ECG = electrocardiogram; ECOG = Eastern Cooperative Oncology Group; GB = glioblastoma; hs-CRP = high-sensitivity C-reactive protein; HVLT-R = Hopkins Verbal Learning Test – Revised; MAP = multi-analyte panel; MDASI-BT = MD Anderson Symptom Inventory-Brain Tumor; MRI = magnetic resonance imaging; PFT = pulmonary function test; PGx = pharmacogenetics; PK = pharmacokinetic; TGF-β = transforming growth factor – beta.

Study Schedule for the continued access period only, Protocol H9H-MC-JBAL

Cycle	Continued Access ^a Visit 501-5XX				Follow-Up ^b Visit 801	Comments
	1±2	6±2	12±2	26±2		
Relative Day Within a Cycle						
Treatment						
Lomustine		X				
LY2157299	X	X	X			
Procedures						
Physical examination	X				X	

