6.11.1. Neurocognitive Function

6.11.1.1. Neurocognitive Outcome Measures

Neurocognitive function will be measured by the HVLT-R, the Trail Making Test, Parts A and B, and COWA. These tests in the neurocognitive test battery will be completed at prestudy (baseline), end of cycle 1 (26 ± 2 days) and thereafter every 2 cycles starting at cycle 2 and after discontinuation of study therapy (Visit 801) during the study.

See table below for the administration time allocated to each test. The MDASI-BT, Trail Making Test Parts A and B, and COWA can be completed during the 20-minute wait before the delayed

recall for the HVLT-R; as a result of the delayed recall, the total time for administration of health outcome measures will be approximately 25 minutes.

Table JBAL.6.11. Cognitive Assessment Tests Used in Study H9H-MC-JBAL

Cognitive Domain	Test	Test Administration Time (minutes)
Memory	Hopkins Verbal Learning Test-Revised (HVLT-R)	5
Cognitive Processing Speed	Trail Making Test, Part A	3
Executive Function	Trail Making Test, Part B	5
Verbal Fluency	Controlled Oral Word Association (COWA)	5

Hopkins Verbal Learning Test-Revised (HVLT-R)

The patient is asked to recall a list of 12 words over 3 learning trials. After a 20-minute delay at the end of the third learning trial, the patient is asked to spontaneously recall the listed words (Delayed Recall trial) read in the 3 learning trials. The Delayed Recognition trial will follow immediately after the Delayed Recall trial and patient is asked to discriminate the listed words from amongst a set of distractors. The total time for this test, exclusive of the delay interval, is 5 minutes. There are 6 alternate forms of this test to minimize practice effects. The test measures learning and memory processes (Benedict et al. 1998).

The scoring for each of the 3 learning trials and the Delayed Recall trial is based on the number of correctly reported words in each trial. For the Delayed Recognition trial, scoring is based on the number of true-positives (listed words correctly recalled) and false-positives (listed words incorrectly recalled).

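### Neurocognitive status: the plan applies a rounded raw-score RCI to the change in standardized score, and codes an unconfirmed decline at the last test as stable

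*SAP*

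**What the plan says.** SAP 6.11.1.2 converts each test to a standardized score (mean 0, SD 1, healthy norms). The categorizing sentence reads: "The change in standardized score from baseline will be calculated and using the Reliable Change Index (RCI"), status over time is classed as improved, stable or declined.

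The threshold is then described on the other scale. The RCI "represents a 90% confidence interval for the difference in raw score between baseline and the next assessment assuming no real change occurred", and SEdiff "is the standard error of difference in raw score from baseline to the next assessment". The next instruction is "All derived RCI will be rounded to the nearest whole number and compared with changes from baseline assessments", which does not say whether those changes are raw or standardized.

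A change has to be confirmed at the next assessment if there is one. Otherwise: "In the absence of a confirmatory assessment, any sign of improvement or decline in neurocognitive status will be deemed as stable".

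On timing, SAP 6.11.1.1 has tests at baseline, at the end of cycle 1, and "thereafter every 2 cycles starting at cycle 2 and after discontinuation of study therapy (Visit 801) during the study". Protocol 10.2 places the tests "at the same time of the disease assessments (ie, MRI) post-baseline, and after discontinuation of study therapy". In Protocol Attachment 1, the table titled "Study Schedule for Protocol H9H-MC-JBAL – Cycles 4, 7, 10, Visit 801, Follow-Up" marks health outcome measures at Visit 801 and none in its Follow Up column.

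The resulting status feeds the per-visit tables, the subgroup proportions and time-in-state analysis (both of which pool stable with improved), and a Cox model whose event is RCI-determined decline or death.

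**The concern.** There are two separate problems.

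**Scale.** The only sentence that names the change to be categorized says standardized, while the threshold is in raw points. A programmer who follows the text compares a quantity with SD 1 against a cut-off of several points, and almost nobody is classed as changed. Putting the RCI on the standardized scale but keeping the whole-number rounding gives a cut-off of 1 SD over much of the plausible reliability range, which also departs from the nominal error rate.

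**Last test.** A decline first seen at Visit 801, or at a patient's only post-baseline test, is coded stable unless some further test, which the plan does not name, is done. In recurrent glioblastoma, the end of treatment is when a real decline is most plausible. Because stable is pooled with improved, such a patient counts as a good outcome. In the Cox analysis the event is deferred to death, or lost if no death is recorded, so the endpoint moves toward OS. Neither document plans a sensitivity analysis for this. SAP 6.10.4 offers only optional alternative censoring dates, within the efficacy section.

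**Working it through.** **The plan's own figure.** Coverage of ±1.64 SEdiff under no real change is 2Φ(1.64) − 1 = 0.899, so the stated 90% reproduces. The one-sided chance of a false decline is Φ(−1.64) = 5.05%.

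**Inputs.** The formulas are from SAP 6.11.1.2: RCI = 1.64 × SEdiff and SEdiff = SD × √(2(1 − r)). The documents give no SD or reliability r for any test, so SD 3 and 5 and r 0.6 to 0.8 are assumptions. Write s = √(2(1 − r)) and k = the rounded raw RCI.

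**Step 1, scale.** The chance that one test flags a true 2-SD decline is Φ((2 − k)/s) when standardized change meets the raw RCI, and Φ((2 − k/SD)/s) when raw change meets the raw RCI.

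| SD | r | RCI | k | Mixed scales | Raw against raw |
|---|---|---|---|---|---|
| 3 | 0.6 | 4.40 | 4 | 1.3% | 77% |
| 3 | 0.7 | 3.81 | 4 | 0.5% | 81% |
| 3 | 0.8 | 3.11 | 3 | 5.7% | 94% |
| 5 | 0.6 | 7.33 | 7 | 1.1e-8 | 75% |
| 5 | 0.7 | 6.35 | 6 | 1.2e-7 | 85% |
| 5 | 0.8 | 5.19 | 5 | 1.1e-6 | 94% |

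Example, SD 5 and r 0.7: s = 0.775, so mixed is Φ((2 − 6)/0.775) = Φ(−5.16), and raw against raw is Φ((2 − 1.2)/0.775) = Φ(1.03).

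**Step 2, rounding on the standardized scale.** With SD = 1 the RCI is 1.47, 1.27 and 1.04 for r = 0.6, 0.7 and 0.8. All three round to 1, and the chance of a false decline, Φ(−1/s), becomes 13.2%, 9.8% and 5.7% instead of 5.05%. At r = 0.5 (cut-off 2) it falls to 2.3%, and at r = 0.9 (cut-off 1) to 1.3%.

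**Step 3, how often the last test matters.** Assume time on treatment is exponential with the lomustine median PFS values in Protocol Table JBAL.5.1 (1.64 months, about 50 days, and 82 days), tests on days 26, 54, 110, 166 and so on, and Visit 801 always done. The share of patients with a single post-baseline test is 1 − 2^(−26/50) = 30% or 1 − 2^(−26/82) = 20%. These patients cannot be scored as declined. The last test makes up 39% or 29% of all post-baseline tests.

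**Step 4, declines recorded.** Simulation on matched raw scales (SD 5, r 0.7, k 6), with a lasting 2-SD decline at progression and Visit 801 at 30 days after stopping. Each cell gives the SAP rule, then the version that also counts last-test declines.

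| Stopping pattern | Median PFS | Visit 801 attended 100% | 70% | 50% |
|---|---|---|---|---|
| At next scan | 50 days | 78% / 87% | 63% / 86% | 52% / 86% |
| At next scan | 82 days | 77% / 86% | 60% / 86% | 49% / 86% |
| Half stop between scans | 50 days | 41% / 86% | 33% / 74% | 28% / 65% |
| Half stop between scans | 82 days | 41% / 86% | 32% / 74% | 26% / 66% |

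**Step 5, deaths and the Cox model.** Post-progression survival is exponential and set so that median OS is 7.1 or 9.8 months (Protocol Attachment 10). The treated arm's progression hazard is multiplied by 0.67.

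| Quantity | SAP rule | Last-test declines counted |
|---|---|---|
| Declines recorded | 22% to 63% | 58% to 79% |
| Deaths as share of composite events | 37% to 78% | 22% to 42% |
| Cox HR | 0.78 to 0.86 | 0.75 to 0.82 |

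Under the SAP rule an unconfirmed decline is deferred to death by a median of 22 to 152 days. The HR difference within a scenario is 0.02 to 0.09. The OS HR in these scenarios is 0.82 to 0.86.

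**Step 6, cost in false declines.** With no true change, the false-decline rate per score is 2% to 4% under the SAP rule and 6% to 8% with last-test declines counted. For at least one of six independent scores it is 11% to 20% against 32% to 39%; at correlation 0.5 it is 9% to 15% against 23% to 28%.

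**The case against.** The scale problem may be a slip of wording. The RCI and SEdiff are both defined in raw score, whole-number rounding makes sense only for raw points, and the comparison sentence does not say standardized. That stands as the likely intent, and under it the mixed-scale figures in step 1 do not arise. It is still not written down, and the composite score in SAP 6.11.1.1 exists only as an average of standardized scores, so a raw-only rule would not cover it if it were categorized. It also stands that rounding on the standardized scale can err in either direction, as step 2 shows.

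The confirmation rule is explicit, prespecified and applied equally to improvement, and it limits false declines. That is a good reason to keep it as the main analysis.

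The blank Follow Up column is weak evidence. It also shows no tumor assessment, although Protocol 10.1.2 continues scans about every 60 days in patients who stop without progression, and the comments column is redacted. Since Protocol 10.2 ties testing to MRI, later tests in those patients are possible. The gap is clearest for patients who have progressed.

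Two of the three subgroups in SAP 6.11.1.2 (progression-free beyond 6 months, and responders) would usually have a later test, so the effect there should be small; it was not quantified. The simulated decline is also placed at progression. Earlier or gradual declines have more chances to be confirmed, and if every patient stops at a scan and attends Visit 801 the loss is only about 9 percentage points.

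**Conclusion.** The concern holds. The SAP names standardized change against a raw, rounded threshold, and it codes unconfirmed last-test declines as stable. Followed as written, both rules misclassify patients.

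The scale conflict decides whether the status analyses work at all, but only on the literal reading; stating raw against raw removes it. The last-test rule has a real but moderate effect: in the assumed scenarios 26% to 78% of lasting declines are recorded, against 65% to 87%, with a Cox HR shift of 0.02 to 0.09. These figures rest on assumed SDs, reliabilities, Visit 801 attendance, stopping patterns, and the size and timing of decline.

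No bias between arms is shown. The outcome is secondary. The standardized-score summaries, the repeated-measures ANOVA and the primary OS analysis do not use the RCI. The change should be made, but it does not affect the trial's main conclusion.

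**What to change.** In SAP 6.11.1.2:

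- Name one scale: either raw change against the raw RCI with rounding, or standardized change against an unrounded standardized RCI. State the source of SD and r for each test, and the direction for the Trail Making Tests, where a longer time is worse.
- Keep the confirmed-decline analysis as specified.
- Report unconfirmed changes at the last assessment as their own category, not as stable.
- Add a sensitivity analysis of time to neurocognitive progression that also counts unconfirmed declines at the last assessment, and show it beside the confirmed version.

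This needs only SAP wording and one extra analysis of data already collected, with no new visits. The downside is the higher false-decline rate in step 6, which is why the added analysis should be a sensitivity analysis and not a replacement.

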6.4. Multiple Comparisons/Multiplicity

No adjustment for multiplicity is planned for this study. The primary analysis will compare the OS distributions for only LY2157299 plus lomustine and placebo plus lomustine. Comparisons between other treatment arms will secondary or exploratory in nature.

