6.11. Health Outcomes/Quality-of-Life Analyses

Patients with at least baseline and 1 post-baseline assessment will be included in the analyses. Compliance with completing the questionnaires will be summarized at the group-level at each assessment period (defined as the number of completed or prorated questionnaires/number of expected questionnaires given those that are still on study).

Each health outcome parameter will be reported independently. Relationships (predictors or prognostic) among these parameters (patient reported symptoms and neurocognitive function) with other clinical parameters such as PS, OS, and disease assessments (based on MRI) may be explored. For example, relationship between change in neurocognitive function and prognostic and/or predictive nature of baseline assessments with OS or the relationship between change in neurocognitive function and change in MRI.

Health resource utilization such as use of psychostimulants, steroids, anti-epileptic medications, etc will be assessed by treatment arms and exploratory analyses adjusting for these covariates may be performed.

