6.11.2.2. MDASI-BT Analyses

The rate of compliance with completing MDASI-BT will be summarized at the group-level at each assessment: prestudy (baseline), end of cycle 1 and thereafter every 2 cycles (26 ± 2 days) starting at cycle 2 and at discontinuation (Visit 801). Compliance is defined as the number of completed questionnaire/number of expected questionnaire to be completed at the time of the study.

For those patients who had completed at least one assessment, descriptive statistics will be provided for the core symptoms, brain tumor symptoms, symptom interference, and symptom groupings (affect, cognition, focal neurologic deficit, treatment-related symptoms, generalized/disease status symptoms, and gastrointestinal symptoms) at each assessment period by treatment arms. This summary will include number of patients in each arm, number of patients with completed questionnaire, mean, standard deviation, median, minimum, maximum scores and change from baseline.

For those patients who completed a baseline and one post-baseline questionnaire, change from baseline on core symptoms, brain tumor symptoms, symptom interference, and symptom groupings will be assessed. Repeated measures ANOVA will be performed to assess the mean differences in change from baseline between treatment arms, adjusting for baseline score if needed. Least squares mean, mean differences, including 95% confidence interval and p-values indicating significant differences between treatment arms will be provided. Plots of mean and standard deviation for core symptoms, brain tumor symptoms, symptom interference, and symptom groupings over time and change from baseline plots will be provided.

The minimally important difference (MID) is used to assess and interpret mean score differences between treatment arms. A minimally important difference of 1.2 (as defined in the MDASI user manual) will be used as a reference in the time to worsening analysis. Data from each treatment

arm will be analyzed using Kaplan-Meier plots with censoring at the last assessment for patients with no worsening. Median time to worsening with 95% confidence interval will be provided. The proportion of patients who experienced a change from baseline score of 1.2 will also be summarized for each treatment arm and compared between treatment arms.

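### SAP 6.11.1.2 compares cognition within subgroups defined by survival, progression or response, and provides for reporting p-values that are significant without providing for the rest

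*SAP*

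**What the plan says.** SAP 6.11.1.2 sets out to relate survival and tumor response to change in cognitive function. This relationship "will also be assessed in subgroups of patients with" PFS above 6 months, OS above 12 months, or an objective response. Within each subgroup, the proportion stable or improved on all tests, or declined on at least one, at 6 months, at 12 months "or at time of response will be provided and summarized for each treatment arm". The next sentence reads: "Significant p-values comparing the proportion of patients with stable or improved tests on all tests will be reported".

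The SAP gives no test, significance level, contrast or adjustment for this comparison. SAP 6.4 adds: "No adjustment for multiplicity is planned for this study".

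The same section also plans analyses that do not select on later outcome:
- a repeated measures ANOVA of change from baseline between arms;
- a Cox model between arms of the time from randomization to confirmed cognitive decline or death from any cause.

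The set for all health outcome analyses is given in SAP 6.11: "Patients with at least baseline and 1 post-baseline assessment will be included in the analyses".

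**The concern.** There are two separate problems.

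**Selection on outcome.** Surviving 12 months, staying progression-free for 6 months and responding are all results of treatment. If one arm prolongs life, its 12-month survivors are a less selected group than those of the other arm. They may then differ in cognition even if the drug does nothing to cognition. This arises only when the arms differ on the defining outcome, and a difference in OS is what the trial hopes to show.

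**Filtering by significance.** A reader who sees one significant p-value, without the non-significant ones, cannot tell how many comparisons were made. In subgroups this small, a result that passes the filter also tends to show a difference well above the true one.

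At stake is the use of these results in later planning. Protocol 8.2 says that the health outcome measures are needed for future Phase 3 designs.

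**Working it through.** The plan states no figure for this analysis, so there is none to reproduce. Randomized numbers, allocation ratio and design HR are redacted, so arm sizes and HRs below are assumptions shown as ranges.

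**1. Subgroup sizes.** Inputs: control median OS of 7.1 and 9.8 months, average 8.5 (Protocol Attachment 10); PFS at 6 months of 24% on lomustine plus placebo in the cediranib trial, and a response rate of 4% on lomustine in the enzastaurin trial (both Protocol Table JBAL.5.1); 30 to 80 patients per arm (assumed).
- OS above 12 months, exponential survival: 2^(−12/7.1) = 0.31 and 2^(−12/9.8) = 0.43. 30 × 0.31 ≈ 9 and 80 × 0.43 ≈ 34 patients per arm.
- PFS above 6 months: 30 × 0.24 ≈ 7 and 80 × 0.24 ≈ 19.
- Objective response: 30 × 0.04 ≈ 1 and 80 × 0.04 ≈ 3.

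**2. Selection on OS above 12 months.** Simulation of 1,000,000 patients per arm. A latent severity f, normal with mean 0 and SD 0.5 or 1.0, drives death, with hazard (ln 2 / 8.5) × exp(f) × HR. It also drives cognition, with probability of stable or improved 1/(1 + exp(−(0.4 − f))). Treatment has no effect on cognition.

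| SD of f | HR | All patients, control / treated | OS > 12 months, control / treated |
|---|---|---|---|
| 0.5 | 1.00 | 59.4% / 59.3% | 64.3% / 64.3% |
| 0.5 | 0.75 | 59.4% / 59.3% | 64.4% / 63.3% |
| 0.5 | 0.60 | 59.3% / 59.3% | 64.3% / 62.5% |
| 1.0 | 1.00 | 58.2% / 58.2% | 72.0% / 71.9% |
| 1.0 | 0.75 | 58.2% / 58.2% | 71.9% / 70.0% |
| 1.0 | 0.60 | 58.2% / 58.2% | 71.8% / 68.5% |

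The arms agree when all patients are used. Within the survivors, a false difference of 1.1 to 3.3 points appears against the longer-living arm. At HR 1 it vanishes, apart from simulation error.

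**3. Number of tests.** Three subgroups and three arm pairs give nine tests, at an assumed two-sided 0.05.
- Upper figure, independent tests each at the full 5%: 1 − 0.95^9 = 0.37. For one arm pair: 1 − 0.95^3 = 0.14.
- Fisher tests (assumed, since none is named), with subgroup shares of 38%, 24% and 4%, a common success rate of 30% to 65% and 20,000 runs. With overlapping subgroups of random size, the chance of any p<0.05 is 10% to 12% at 30 per arm, 11% to 12% at 37 per arm, 12% to 13% at 37/74/37, and 15% to 16% at 74 per arm. With subgroup sizes fixed at their expected values it is 5% to 8% at 30 per arm, 9% to 10% at 37 per arm, and 13% to 16% at 37/74/37. About 11% to 16% is a fair summary, and less is possible in the smallest case.

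**4. Effect of the filter.** Assume true proportions of 50% and 65%. Fisher power is about 6% with 15 patients per arm and 14% with 25. Among significant results, the mean absolute difference is 50 and 37 points, against a true 15.

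**The case against.** The strongest reply has five parts.

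- **The word "only" is not in the SAP, and the results themselves are not suppressed.** A reader might infer selective reporting of results. The documents do not support that: the proportions are to be given for every arm whatever the p-value. What remains is narrower. The only provision for p-values here covers significant ones, and no other text promises the rest.
- **The contrast is not named.** The stated aim is an association between clinical outcome and cognition, so the p-values might compare subgroups rather than arms. This is fair. But the proportions are tabulated by arm, which makes the between-arm reading natural, and a comparison between outcome groups would be confounded too. The ambiguity itself needs resolving.
- **Better analyses are planned in the same section.** This stands, and it limits the harm. They still require a baseline and one post-baseline test, but that is a much weaker selection than surviving 12 months. They do not remove the subgroup comparison, which the SAP still calls for.
- **37% is too high.** This stands. The subgroups overlap, the arm pairs share patients, and exact tests on small groups fall short of 5%.
- **The symptom analysis is sound.** A reader might extend the point to the MDASI-BT because of the wording "p-values indicating significant differences between treatment arms will be provided" in SAP 6.11.2.2. The same sentence provides least squares means, mean differences and 95% confidence intervals, and those analyses are not run in outcome-defined subgroups. The point does not reach them.

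**Conclusion.** The point holds for SAP 6.11.1.2 alone. As written, the section invites a between-arm comparison that randomization does not protect, with p-values provided for according to whether they are significant.

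The selection bias is modest: about 1 to 3 points for the OS subgroup under the assumed severity models and HRs of 0.60 to 0.75, and none if survival is equal. It would be too strong to say that the longer-living arm must show worse cognition, because the size and direction depend on how severity links to both outcomes. The chance of at least one false positive among nine tests is about 11% to 16% under the Fisher assumptions, with 37% as a ceiling.

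This is a subsidiary health outcome analysis. The primary OS inference is unaffected. The change is worth making because it costs almost nothing and the results are meant to inform later trials.

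**What to change.** Amend SAP 6.11.1.2 only.

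1. Keep the three outcome-defined subgroups as description by arm, without between-arm p-values. If a comparison is kept, name the contrast, the test and the significance level, and report the estimate, 95% CI and p-value for every comparison regardless of significance, labelled exploratory and not causal.
2. State that between-arm conclusions on cognition rest on the planned whole-arm analyses, mainly the Cox model of neurocognitive decline or death.

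A composite of alive and cognitively stable at 12 months is not a workable substitute. Under SAP 6.11.1.1 and Protocol Attachment 1, no cognitive tests are scheduled after Visit 801, about 30 days after treatment ends. Many patients alive at 12 months would have no test near that time.

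The cost is a short wording change, plus a few more table rows if comparisons are kept, or the loss of the subgroup p-values if they are not.
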